4.5 Missing Data and Partial Dates

Unless stated otherwise, missing data will not be replaced with imputed values.

Partial start or stop dates (month or day) are allowed on CRF for adverse events, concomitant medication, antipsychotic medication, and medical history. An entry for the year is required in the eCRF system for each of these dates. Only the month and day may be entered as unknown. Dates from these forms will be reported in listings as collected. Every effort will be made to query missing dates.

For records with a partial start date, the following procedure will be employed in determining if an AE is treatment emergent AE:

- Dates with missing day and non-missing month will be assumed to occur on the first day of the non-missing month, except for assessments/events occurring in the first month of dosing, in which case the date will be the first day of dosing.
- Dates with missing month will be assumed to occur on the first day of the non-missing year (i.e. January 1), except for assessments/events occurring in the first year of dosing, in which case the date will be the first day of dosing.

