12.6 Reporting Procedures for All Adverse Events

All AEs (including SAEs) occurring during the trial will be reported on the running logs in the AE section of the eCRF. This includes all events from the time following screening up to and including the post-trial follow-up visit, whether or not attributed to IMP and observed by the investigator or patient.

The following information will need to be provided for all AEs:

A) Adverse Event (Diagnosis or Syndrome if Known, or Signs and Symptoms)

Where the investigator cannot determine a diagnosis, signs or symptoms should be recorded in the AE section of the eCRF. Once a diagnosis has been determined the AE section of eCRF must be updated to reflect the diagnosis in replacement of the original symptoms. In circumstances where only a provisional diagnosis is possible (working diagnosis), the eCRF must be updated to reflect the provisional diagnosis in replacement of the original symptoms. In some circumstances it may be relevant for the investigator to include the symptoms alongside the diagnosis in the verbatim event description. However, the diagnosis (full or provisional) should be clearly stated, e.g., fever and malaise due to respiratory tract infection.

B) Adverse Event Start Date and Stop Date

The start and stop dates of the event must be provided. All AEs require these fields to be completed in full. Partial dates or missing dates are not normally acceptable and significant effort must be undertaken to obtain any unknown information. If a precise date is not known an estimated date should be provided instead. When a complete date cannot be given, record as much information as possible (i.e., month and year or, in exceptional circumstances, just year). When the actual start date becomes known the eCRF must be updated to replace the previously recorded date.

C) Outcome

The outcome of the event must be recorded accurately and classified into one for the following categories:

- Recovered/Resolved.
- Recovered/Resolved with Sequelae.
- Not Recovered/Not Resolved.
- Fatal.

D) Severity

When describing the severity of an AE the terms mild, moderate, or severe should be used. Clinical judgment should be used when determining which severity applies to any AE.

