8.2 Adverse Events

Adverse events will be collected from the date caregiver signs informed consent form up to the post-treatment safety follow-up visit. All AEs occurring during the trial, whether attributed to the IMP or not, observed by the investigator, or reported by the caregiver, will be recorded in the eCRF. AEs will be coded using the latest version of MedDRA at the time of reportig, associating lower-level terms with preferred terms and system organ classes by the primary hierarchy. Treatment-emergent AEs (TEAEs) are AEs that started, or worsened in severity or seriousness, following the first dose of IMP.

An AE profile for the Safety analysis set will be provided, which summarizes the subject incidence by treatment received, for the following information:

- Any TEAEs
- TEAEs related to treatment
- Serious TEAEs
- Serious TEAEs related to treatment
- TEAEs leading to withdrawal of IMP
- TEAEs related to treatment leading to withdrawal of IMP
- TEAE leading to death

AE summaries will include TEAEs. AE descriptions will be presented by decreasing frequency across all patients for a given SOC and Preferred Term. The tables will display counts and percentages of subjects who reported at least one AE in each system organ class represented in the AE data. Within each system organ class, the tables will display the counts and percentages of subjects reporting at least one AE, as designated by the preferred terms.

The following AE summaries will be produced:

- TEAEs by SOC and PT
- TEAEs related to treatment by SOC and PT. This table will include TEAEs that have a plausible relationship to the IMP as assessed by the investigator.
- TEAEs by SOC, PT, and maximum severity. On this table, treatment groups will be subdivided into three potential grades of AE severity— Mild, Moderate, Severe. TEAEs missing a severity grade will be imputed as 'Severe'.
- TEAEs by SOC, PT, and sex
- TEAEs by SOC, PT, and time of first onset (<1 week, 1-<4 weeks, 4-<12 weeks, >=12 weeks)
- TEAEs by SOC, PT, and time to AE resolution (<1 week, 1 week, 2 weeks, 3 weeks, 4 weeks, >=5 weeks, ongoing).
- Serious TEAEs by SOC and PT
- Serious TEAEs related to treatment by SOC and PT. The same approach applies as described for TEAEs related to treatment.
- TEAEs leading to study withdrawal by SOC and PT. This subset includes "Study Discontinuation" due to TEAEs.

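### The SAP's partial-date rule ignores the AE stop date, so an event with a partial start in the month or year of first dose is classed as treatment-emergent even when it ended before dosing

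*SAP*

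**What the plan says.** SAP 4.5 introduces its rule with "For records with a partial start date, the following procedure will be employed in determining if an AE is treatment emergent AE". It has two bullets:

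- Day missing, month known: the start is taken as the first of that month, "except for assessments/events occurring in the first month of dosing, in which case the date will be the first day of dosing".
- Month missing: the start is taken as 1 January, "except for assessments/events occurring in the first year of dosing, in which case the date will be the first day of dosing".

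Neither bullet mentions the stop date. The same section sets the general default: "Unless stated otherwise, missing data will not be replaced with imputed values". It also confirms that "Partial start or stop dates (month or day) are allowed on CRF for adverse events".

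On collection, SAP 8.2 says "Adverse events will be collected from the date caregiver signs informed consent form up to the post-treatment safety follow-up visit". Protocol 12.6 says "The start and stop dates of the event must be provided", and then "When a complete date cannot be given, record as much information as possible (i.e., month and year or, in exceptional circumstances, just year". It also says that partial dates are not normally acceptable and that an estimated date should be given when the exact one is unknown.

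SAP 8.2 and Protocol 13.6.3.2 define a TEAE in the same way: an event with onset, or with worsening in severity or seriousness, after the first dose.

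**The concern.** Placing an ambiguous start on the first dosing day is a common conservative choice. It is reasonable when the data cannot show whether the event began before or after treatment. Here the rule also applies when the data do show it: an event whose recorded stop date precedes the first dose cannot have started after that dose. The rule still calls it treatment-emergent, which contradicts the plan's own definition.

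At stake is the accuracy of the all-causality TEAE outputs in SAP 8.2: the overall AE profile, the SOC and preferred-term tables, and the severity, sex and serious-event tables. Each affected record would be a pre-treatment event reported as occurring on GWP42003-P or placebo.

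**Working it through.** The plan gives no figure on this point to reproduce. The check applies the written rule to example dates and then asks how much of the pre-dose period the exception covers.

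**1. Can the case arise?** Consent is at Visit 1, and randomization follows 7 to 14 days later (Protocol 4.1, SAP 3.1). The first dose is taken at home on the evening of Visit 2 (SAP 4.2). AE review is scheduled at Visits 1 and 2 (Protocol Appendix 1). Every patient therefore has an untreated period in which AEs are recorded, and the form allows partial dates.

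**2. Does the worsening part of the TEAE definition cover it?** No. Protocol 12.5 requires a new event record when a pre-treatment event worsens after the first dose. A record that closed before dosing cannot qualify through worsening.

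**3. The rule applied.** Assume a first dose on 20 June 2021, and read the first month of dosing as the calendar month of the first dose.

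| Recorded start | Recorded stop | Start under SAP 4.5 | Class under SAP 4.5 | Class with a stop-date check |
|---|---|---|---|---|
| June 2021, day missing | 15 June | 20 June | TEAE | Not a TEAE |
| June 2021, day missing | 19 June | 20 June | TEAE | Not a TEAE |
| 2021, month missing | 12 June | 20 June | TEAE | Not a TEAE |
| May 2021, day missing | 30 May | 1 May | Not a TEAE | Not a TEAE |
| May 2021, day missing | 10 June | 1 May | Not a TEAE | Not a TEAE |
| June 2021, day missing | 20 June | 20 June | TEAE | TEAE |
| June 2021, day missing | Ongoing | 20 June | TEAE | TEAE |

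The first three rows are misclassified. The two rows with a start in May are classed correctly, so the fault is confined to partial starts in the month (or, for a missing month, the year) of first dose. The stop-date check corrects the three wrong rows and changes none of the others.

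**4. Share of the pre-dose period open to the exception.** Let the first dose fall on day d of a 30-day month, with d uniform on 1 to 30 (assumption), and let the pre-dose window be w days. The number of window days in the month of first dose is min(d − 1, w). The average share is the sum of min(d − 1, w) over d = 1 to 30, divided by 30w.

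- w = 7: (21 + 23 × 7) / 210 = 182/210 = 0.867
- w = 10: (45 + 20 × 10) / 300 = 245/300 = 0.817
- w = 14: (91 + 16 × 14) / 420 = 315/420 = 0.750

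For the missing-month rule, with first doses spread evenly over a 365-day year (assumption), the share of pre-dose days in the year of first dose is 1 − (w + 1)/(2 × 365). This gives 1 − 8/730 = 0.989 for w = 7 and 1 − 15/730 = 0.979 for w = 14.

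These are shares of days. An AE is affected only if its start date is also partial, it resolved before dosing, and its stop date is complete enough to show that.

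**The case against.** **The case should be rare.** Protocol 12.6 discourages partial dates and asks for an estimate, SAP 4.5 promises queries, and year-only dates are for exceptional circumstances. A pre-dose event that has ended would normally be recorded by Visit 2, while recall is fresh. For SAEs, entry within 24 hours of discovery or notification (Protocol 12.3) makes a missing start day unlikely. All of this stands. It limits the count but does not make the rule correct.

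**Conservative imputation is standard practice.** True for ambiguous dates, and the check leaves those alone: ongoing events and events ending on or after the first dosing day stay treatment-emergent. Where the stop date settles the order, no ambiguity remains to be conservative about.

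**Programmers would add the check anyway.** They would then depart from a written SAP rule, and Protocol 13 requires deviations from the SAP to be described in the study report.

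**Related-event tables are largely protected.** Protocol 12.5 has events that start before the first dose treated as not causally related. This stands, and it confines the effect mainly to the all-causality tables.

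A reader might infer two stronger things:

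- *Affected events get a negative duration and fall into the shortest class of the time-to-resolution table.* The SAP does not say so. The imputation is stated only for deciding treatment-emergent status, and the default is no imputation. On the text, the duration would be missing. A zero or negative value arises only if the imputed start is carried into that table, for which the SAP gives no formula.
- *The error biases the comparison by pulling the arms together.* The rule is the same in both arms, and randomization balances pre-dose events in expectation. Adding similar expected counts to each arm dilutes a ratio but leaves the absolute difference roughly unchanged. The TEAE presentations are descriptive.

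**Conclusion.** The point holds in a narrow form. As written, SAP 4.5 classes as treatment-emergent an AE whose stop date shows that it ended before the first dose, whenever its partial start falls in the month of first dose (day missing) or the year of first dose (month missing). This is a stated rule that gives a wrong result, and the stop date needed to avoid it is already collected.

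Under the even-spread assumptions, 75% to 87% of pre-dose days are open to the missing-day exception, and about 98% to 99% to the missing-month exception. Neither range measures affected AEs. That number cannot be derived from the documents and is probably small. No efficacy result depends on the rule. This is a minor correction to safety reporting.

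**What to change.** Add to both bullets of SAP 4.5: *unless the AE stop date, complete or partial, shows that the event ended before the first dose, in which case it is not treatment-emergent*. A partial stop date matters mainly when the start month is missing, for example a stop month earlier than the month of first dose.

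Also state in SAP 8.2 whether imputed start dates are used in the time-of-onset and time-to-resolution tables. If they are, add that an imputed start may not be later than the stop date. If they are not, say how events with partial starts appear in those tables.

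The cost is two or three sentences in the SAP and one condition in the TEAE derivation. No new data are needed, and the classification of ambiguous and ongoing events does not change.

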4.6 Multiple Study Centers

The study will be conducted at multiple centers in North America and Rest of the World. Data from all sites will be pooled for all analyses. For efficacy analyses, region (North America, Rest of the World) will be included as a stratification factor.

5. Statistical Analysis

5.1 Hypothesis testing

Statistical hypothesis testing will be performed on the efficacy and exploratory endpoints as appropriate with no inferential statistical decision drawn as this is an exploratory trial. Statistical hypotheses will be tested using 2-sided tests at a 5% significance level. P-values and 95% confidence intervals will be provided where appropriate.

5.2 Analysis Populations

Five analysis populations will be defined for use with various analyses. Table 2 illustrates the relationship between each population and the analyses for which the data from the population will be used.

Table 2 Analysis Populations

		Analysis Population			
Analysis	Screened Analysis Set	Full Analysis Set	Safety Analysis Set	Per Protocol Analysis Set	
Subject disposition	X		X		
Population inclusion	X	X			
Medical history		Х			
Autism history		X			
Caregiver		X			
Demographics and baseline characteristics		Х	Х	Х	
Protocol deviations	X	X			
Efficacy endpoints		X		X	
Safety endpoints			X		

5.2.1 Screened Analysis Set

The Screened analysis set includes all subjects who are enrolled (i.e, screened in the trial by providing written informed consent/assent).

5.2.2 Full Analysis Set (FAS)

All patients who have been randomized to study treatment and receive at least 1 dose of IMP will be included in the full analysis set (FAS) irrespective of their protocol adherence and continued participation in the study. Patients will be analysed according to their randomized IP assignment, irrespective of the treatment actually received.

5.2.3 Safety Analysis Set

All patients who receive at least 1 dose of IMP in the trial will be included and analyzed according to the treatment received. Only patients for whom it has been confirmed that they did not take any IMP will be excluded from the safety analysis set.

5.2.4 Per Protocol (PP) Analysis Set

The PP set is defined as all patients that are a subset of the FAS who have no major protocol deviations deemed to compromise the assessment of efficacy. Major protocol deviations will be identified and fully defined prior to unblinding of the trial based on the blinded data. A patient may be considered to be excluded from the PP set if any of the following criteria are met:

- Not meeting Inclusion criteria, or meeting Exclusion criteria
- Usage of restricted medications/treatments that may affect interpretation of the efficacy endpoints
- Noncompliance with the trial treatment regimen
- Incorrect treatment administered to/taken by subject

Alternate criteria for exclusion from the PP set may be applied to accommodate unforeseen events that occurred during the conduct of the study. The subjects belonging to PP analysis set are defined prior to breaking the blind of the study in a blind data review meeting.

6. Data Display Characteristics

Unless stated otherwise in relevant sections to follow, continuous data will be summarized with the number of non-missing values (n), mean, standard deviation (StdDev), minimum (min), median, and maximum (max). Categorical variables will be summarized by the frequency and proportion of participants falling into each category.

Unless stated otherwise, data listings will be produced for all recorded data. Data listings will be ordered by treatment, site, subject number, and time of assessment. When expedient, additional levels of ordering hierarchy may reflect subsets of assessments within subject. Additional data listings will be produced for outcome measures that involve extensive procedures to derive the analyzed outcomes.

Figures will be produced when specified in sections to follow.

Details of the display format and numbering will be described in a separate TLF shells document.

The MedDRA version used for coding AEs, prior/concomitant medications and laboratory parameters will be included in the relevant outputs as a footnote.

All summaries, statistical analyses, data listings, and figures will be completed using SAS version 9.4 of the SAS Institute (North Carolina, USA) unless otherwise noted. Each summary, figure, or data listing will include the data cutoff date in addition to the production date.

6.3 Subject Accountability

6.3.1 Disposition

The presentation of patient disposition will include information on enrolment, randomization, receiving at least one dose of IP, completing Week 4, Week 8 and Week 12 of treatment and study discontinuations and completing the study. Number of subjects completed the follow up period and tapered the medication will be included. It will summarise whether a subject did or did not experience these milestones and, if not, the reason. The presentation will also include the number of subjects with complete follow-up of each efficacy endpoint and vital status of subjects at the end of the study (dead, alive or unknown). The tabulation will include an overview

of the number and percentage of subjects experiencing a particular disposition event, per treatment arm and in total, with number of randomized subjects in the respective treatment group, and in total, used as the denominator for the percentage calculation. Number of subjects enrolled, but not randomized, as well as number of subjects with a certain reason for not being randomized will only be displayed for all subjects combined, with no percentage calculated. The number and percentage of subjects discontinuing treatment and discontinuing study due to COVID-19 will also be presented.

The disposition data mentioned above will be listed for all patients.

6.3.2 Subject Characteristics

Data collected about the following subject characteristics at the Baseline visit (Visit 2) will be summarized for populations as in Table 2.

Demographics

The following demographic and baseline characteristics data will be summarized by treatment group and overall using the safety set.

Demographic characteristics: age at randomization, age group (6 to 11, 12 to 17), sex at birth, if female, childbearing potential, race and ethnicity.

Baseline characteristics: height (cm), weight (kg), body mass index (BMI) (kg/m2). use of antipsychotics, region and WASI-II (verbal comprehension index score (VCI); perceptual reasoning index score (PRI); intelligent quotient score (FSIQ-2)).

Medical history

Previous and current medical conditions (excluding autism history) will be summarized as the numbers and percentages of subjects for the FAS by system organ class (SOC) and preferred term (PT).

Autism history and diagnosis

Autism diagnosis will be summarized for the FAS as per eCFR form "Autism History" and in addition, assessment used to confirm diagnosis (ADOS-2, ADI-R). Time since initial diagnosis (number of years from date of original diagnosis to the date of informed consent/assent) will also be presented.

- ADOS-2. Module administered; Social Affect Total; RBR/RRB Total; Overall Total;
- ADOS-2 Comparison Score; ADOS-2 Classification.
- ADI-R. Scores for A, B, C, D.

Autism history events will be summarized as per cetegories presented in the eCRF.

Main caregiver and caregiver update

Caregiver information as collected at Visit 1 on the "Main Caregiver" eCRF will be summarized using FAS. Changes to caregiver collected at each visit will be summarise and also will present how many patients had changed the caregiver.

6.3.3 Protocol Deviations and Population Inclusions

All screened patients will be displayed in a listing that includes eligibility for each analysis set, protocol version for which patient was enrolled, dates of informed consent/assent and screening.

All protocol deviations are recorded in the Clinical Trial Management System, InfoLink2, and will be included in a data listing of deviations.

Major protocol deviations resulting in FAS subjects being excluded from the PP set will be summarized by deviation category.

7. Efficacy Analyses

Efficacy analyses, constituting the comparison of GWP42003-P against placebo in reducing symptom severity in children with ASD, will use data from the FAS and the PP analysis set as specified in Table 2.

Statistical hypothesis testing will be performed with no inferential statistical decision drawn as this is an exploratory trial. Unless otherwise specified, for all analyses for which a statistical test is performed, the null hypothesis corresponds to no difference between GWP42003-P and Placebo treatment arms.

Example SAS-codes provided may be modified without amendment to this SAP.

7.1 Statistical Models

7.1.1 MMRM analysis

The change from baseline of the VABS, ABC and RBS endpoints will be analyzed using an MMRM model. The corresponding model will include randomization stratification factors, baseline score, visit, treatment arm, visit by treatment arm interaction, visit by baseline interaction as fixed effects, and visit repeated within each patient as a repeated effect.

LS mean estimates for each treatment arm at each visit, along with the standard error and 95% CI will be presented separately. In addition, estimates of the treatment difference at each visit will be presented along with standard errors of difference and 95% CIs. The main comparison of interest is the estimate of the treatment difference at Week 12 (Visit 8).

The following provides sample code for implementing MMRM analysis using compound symetry covariance matrix:

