13.6.1 Efficacy Endpoints

13.6.1.1 VABS-3

The VABS-3 social and communication composite (arithmetic mean of the social and communication domain scores), the adaptive behavior composite, and individual domain scores will be analyzed. The VABS social and communication composite score is a key interest.

The change from baseline in social and communication composite score for VABS-3 will be summarized by treatment arm and visit.

The change from baseline in social and communication composite score for VABS-3 will be analyzed in the final analysis using an MMRM model. The corresponding model will include randomization stratification factors, baseline composite score, visit, treatment arm, visit by treatment arm interaction as fixed effects, and visit repeated within each patient as a repeated effect. An unstructured covariance matrix will be used to estimate the variance-covariance structure within patients across time points. If convergence is not obtained, then other covariance structures to be used will be specified in the SAP. Objective criteria for assessing normality assumptions and proposed alternative analyses will be specified in the SAP.

A Bayesian evaluation will also be carried out on the final data (see also Section 13.2).

From this analysis the LS mean estimates for each treatment arm at each visit, along with the standard error and 95% CIs will be presented separately. In addition, estimates of the treatment difference at each visit will be presented along with standard errors of the difference and 95% CIs. The main comparison of interest is the estimate of the treatment difference at Week 12.

The change from baseline in adaptive behavior composite score and for each individual domain will be summarized and analyzed as described above for the social and communication composite score.

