13.6.1.2 ABC

All ABC subscales will be analyzed. The ABC-I subscale is of key interest.

ABC-I subscale scores will be summarized by treatment arm and visit together with the corresponding change from baseline scores.

The change from baseline in ABC-I scores will be analyzed separately using a similar model as the one described for the social and communications composite endpoint.

The other ABC subscales will be summarized and analyzed as described for the ABC-I subscale.

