7.1.4 ANCOVA model

An ANCOVA model with randomization stratification factors and treatment arm as factors and baseline score as a covariate will be used to analyze change from baseline to Week 12. The LS mean estimates for each treatment arm will be displayed together with standard errors and their corresponding 95% CIs. Treatment differences with 95% CIs will also be produced.

The following provides sample code for implementing ANCOVA analysis:

```
ods output lsmeans=lsmeans diffs=diffs;
proc mixed data=test;
  class trt randager randrgn randpsy;
  model chg = base trt randager randrgn randpsy / ddfm=kr cl
  alpha=0.05 solution;
  lsmeans trt / cl diff;
run;
```

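### The protocol sets an unstructured covariance for the key VABS-3 MMRM, but the only structure named in SAP 7.1.1 is compound symmetry, which can miscalibrate the Week 12 interval and p-value

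*SAP*

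**What the plan says.** Protocol 13.6.1.1 specifies the MMRM for the VABS-3 social and communication composite and fixes its covariance: "An unstructured covariance matrix will be used to estimate the variance-covariance structure within patients across time points". The one exception follows directly: "If convergence is not obtained, then other covariance structures to be used will be specified in the SAP". Protocol 13.6.1.2 then has the change in ABC-I "analyzed separately using a similar model as the one described for the social and communications composite endpoint".

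SAP 7.1.1 covers these endpoints together: "The change from baseline of the VABS, ABC and RBS endpoints will be analyzed using an MMRM model". It lists the fixed effects and the repeated visit effect, and makes the Week 12 (Visit 8) treatment difference the main comparison. That description names no covariance structure. One appears only where the sample code is introduced: "The following provides sample code for implementing MMRM analysis using compound symetry covariance matrix". The code itself is not in the public text.

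SAP section 7 (Efficacy Analyses) says of all such code: "Example SAS-codes provided may be modified without amendment to this SAP". SAP 7.1.2 states that the GEE results rest on empirical standard errors. No similar statement is legible for the MMRM. The SAP's table of changes from the protocol survives only in fragments, and no weight is placed on it here.

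**The concern.** The protocol left one covariance matter to the SAP: which structures to use if the unstructured model does not converge. The legible SAP does not restate unstructured as primary, gives no fallback order, and names compound symmetry without linking it to non-convergence. An analyst who takes the lead-in at face value departs from the protocol for VABS-3. An analyst who treats the code as changeable finds nothing in the SAP text that fixes the structure, so it could be chosen after unblinding without an SAP amendment.

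The choice matters because both endpoints of key interest, the VABS-3 composite and ABC-I, are judged at one visit. Compound symmetry gives Weeks 4, 8 and 12 a common variance. With model-based standard errors, the Week 12 standard error is then built from the average variance over the three visits. If the true Week 12 variance is above that average, the 95% CI is too narrow and the p-value too small. If it is below, the reverse holds. If they match, nothing is lost.

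**Working it through.** **The plan's own figure.** Protocol 13.1 assumes SD 8.46, a 4-point difference and a two-sided 0.05 test. By the normal approximation, n per arm = 2 × (1.96 + 0.8416)² × 8.46² / 4² = 70.2, so 71. The stated 72 gives 81.0% power (80.4% with the t distribution), and 144 / 0.9 = 160. The sample-size statement reproduces and is not in question.

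**Inputs.**
- From protocol 13.1: 72 evaluable patients per arm, SD 8.46 (taken here as the Week 12 residual SD), a 4-point difference.
- From SAP 7.2.1: three post-baseline VABS-3 assessments (Visits 5, 7 and 8, that is Weeks 4, 8 and 12).
- Assumed, because the documents give a single common SD: the Week 4 and Week 8 SDs, and the between-visit correlations used in simulation.

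**Formulas (complete data, treatment-by-visit terms).** The Week 12 estimate is the same under either structure. Only its standard error changes.
- True SE = 8.46 × √(2/72) = 1.41. Correct 95% half-width = 1.96 × 1.41 = 2.76.
- Compound symmetry replaces the Week 12 variance by the mean of the three visit variances, so r = SE(CS) / SE(true) = √(mean visit variance / Week 12 variance).
- Type I error = 2 × [1 − Φ(1.96 r)]. Half-width = 2.76 r.
- Power at 4 points = 1 − Φ(1.96 r − 4/1.41).

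**Worked case, SDs 6 / 7.3 / 8.46.** Variances are 36, 53.29 and 71.57, with mean 53.62. Then r = √(53.62/71.57) = 0.866, 1.96 r = 1.70, and type I error = 9.0%.

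| SD at Weeks 4 / 8 / 12 | r | Type I error, formula | Type I error, simulated | 95% half-width |
|---|---|---|---|---|
| 7.5 / 8 / 8.46 | 0.945 | 6.4% | 6.2% | 2.61 |
| 6 / 7.3 / 8.46 | 0.866 | 9.0% | 9.1% | 2.39 |
| 7 / 9.7 / 8.46 | 1.000 | 5.0% | 5.0% | 2.76 |
| 9.3 / 8.9 / 8.46 | 1.051 | 3.9% | 3.7% | 2.91 |
| 10 / 9.2 / 8.46 | 1.092 | 3.2% | 3.0% | 3.02 |
| 8.46 / 8.46 / 8.46 | 1.000 | 5.0% | 5.0% | 2.76 |

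In the second row, coverage is 91.0%. In the fifth, power at 4 points is 1 − Φ(2.141 − 2.837) = 75.7%, against 81.0% at r = 1. The third row shows that unequal variances do no harm when Week 12 happens to sit at the average.

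**Simulation behind the table.** 20,000 null trials per scenario, 72 per arm, complete data, no covariates, correlation 0.7 between adjacent visits and 0.49 between Weeks 4 and 12. The Monte Carlo standard error is √(0.05 × 0.95 / 20,000), about 0.15 percentage points. In the same scenarios the unstructured model rejected 4.6–5.1% of the time, and empirical standard errors gave 4.8–5.2%.

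**Closer to the planned model.** A REML fit with 160 patients, 10% completely random dropout, the SAP's fixed effects and adjacent-visit correlation 0.6 was run 2,000 times per scenario (Monte Carlo standard error about 0.5 points). Compound symmetry rejected:
- 4.4% with equal SDs;
- 6.1% with 7.5 / 8 / 8.46;
- 9.2% with 6 / 7.25 / 8.46;
- 2.9% with 10 / 9.2 / 8.46, where power at 4 points was 75.0%.

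In a 250-trial comparison at 6 / 7.25 / 8.46, unstructured rejected 4.4%, with mean SE 1.396 against an empirical SD of 1.394. Compound symmetry on the same data rejected 8.8%, with mean SE 1.202.

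**The case against.** The strongest reply is that text is missing exactly where the answer might be. The code after the lead-in is absent and could hold an empirical standard-error option or a note on alternative structures. This stands as a limit: the miscalibration claim is conditional on model-based standard errors, and nothing is claimed about the unseen code. It does not remove the mismatch, because the lead-in itself names compound symmetry and the surrounding model description names nothing.

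A second reply is that the SAP is silent on structure, so the protocol governs, and compound symmetry is the non-convergence fallback it delegated. That reading is possible, but the legible SAP does not state it. If it was intended, one sentence settles the matter.

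Other points also stand in part:
- The protocol is explicit about unstructured covariance for VABS-3 only. For ABC-I it asks for a similar model, so carrying the structure over is a natural reading but not a literal requirement.
- The sizes are illustrative. The 9.0% case needs the variance to about double between Weeks 4 and 12 (36 to 71.6), and the mild case gives 6.4%.
- Empirical standard errors are not in the protocol. They are recommended here only for structures that force equal visit variances.
- The trial is exploratory and draws no inferential decision, so the damage is to reported precision and nominal p-values, not to a formal test.

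**Conclusion.** The concern holds. The protocol names an unstructured matrix for the key VABS-3 model, while the only structure legible in SAP 7.1.1 is compound symmetry, with no tie to non-convergence. Under compound symmetry with model-based standard errors, the illustrated Week 12 type I error runs from 3.2% to 9.0% and the CI half-width from 3.02 to 2.39 points, against a correct 2.76. There is no effect when the Week 12 variance equals the visit average. These figures rest on assumed Week 4 and Week 8 SDs and on reading 8.46 as the Week 12 residual SD. The direction in this trial cannot be told from the documents. The only dropout examined was 10%, completely at random; nothing is claimed about other patterns. The point should be fixed, because intervals and p-values will be reported for both key endpoints even though no formal decision follows.

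**What to change.** Before unblinding, revise the text of SAP 7.1.1, not only its sample code:

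1. Name unstructured covariance as the primary structure for the VABS-3 MMRM, as in protocol 13.6.1.1, and apply it to ABC-I as well.
2. State the degrees-of-freedom method. Kenward-Roger is suitable. The SAP's ANCOVA code already requests it ("model chg = base trt randager randrgn randpsy / ddfm=kr cl"), although that is a single-time-point model and so only a weak precedent for the MMRM.
3. List fallback structures in order, for use only on non-convergence, with empirical (sandwich) standard errors for any that force equal visit variances, such as compound symmetry.
4. If compound symmetry is really meant as primary, record it with a reason under the SAP's changes from the protocol, and use empirical standard errors.

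The cost is a few lines of text and one code option. Three post-baseline visits need 3 × 4 / 2 = 6 covariance parameters, which is modest for 144 to 160 patients. Sample size, visits and the treatment effect being estimated are unchanged.
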